The Effect of Temporal Muscle Suspension on the Risk of Temporal Hollowing:
A Prospective Randomized Clinical Trial

[name]
Associate Professor
Department of Plastic and Reconstructive Surgery
Johns Hopkins School of Medicine

Johns Hopkins Hospital
[name]
[name]
[contact]
[contact]

Application No. : IRB00120812

The pterional approach to the cranio-facial region is an often-used approach by neurosurgeons. This surgical approach is used for access to intra-cranial abnormalities (ie. Tumors, trauma, or vascular insults). Temporal hollowing is a common complication that that can affect the patient both physically and emotionally. In an aesthetic region, it can represent a stigma of disease that prevents the patient from moving on with the normalcy of their disease-free lives. The hollowing generally occurs within 6 months from the index surgery. Currently the exact mechanism or incidence of this complication is not very well described.

The purpose of this prospective study is see if traditional techniques to the closure and temporal muscle suspension (TMS) after the pterional approach will show any differences in post-operative temporal hollowing (TH).

1. Objectives

The primary objective is to identify which patients undergoing a traditional pterional approach with 2 different surgical techniques for TMS will develop TH. Pre and post-operative CT scans will be reviewed and analysis with previously proven metrics will be performed.

2. Background

Surgical Details/Anatomy

The pterional approach is an indicated neurosurgical approach commonly used for anterior circular aneurysms, suprasellar lesions, and medial sphenoid wing tumors (1,2). A curvilinear incision from the midline widows peak and extending laterally to 1 cm anterior to the tragus of the ear, terminating within a skin crease, with preservation of the superficial temporal artery if possible. The temporalis fascia is encountered and divided. Either the entire temporalis muscle can be elevated or a cuff of temporalis muscle can be left on the cranium to facilitate closure and suspend the temporalis muscle. Subperiosteal dissection of the muscle is performed and the craniotomies are then accomplished. Reconstruction of the pterional approach can be accomplished with bony fixation of the bone flap. However, the TMS can be performed by:

Date: 10/24/2017
Principal Investigator: [name]
Application Number: IRB00120812

1. Resuspension of the temporalis muscle to the cuff of muscle left on the temporal crest
or
2. Suturing the temporalis muscle directly to one of the bone plates that is used to for
fixation.

Current Literature

The TH can occur either due to direct injury to the muscle, atrophy from denervation or even loss of vascular supply (3). Modern neurosurgical techniques have led to great improvements of surgical and functional outcomes, however less attention has been paid to the post-operative complications of scarring and soft tissue deformities (4). There have been several techniques and alterations to the traditional pterional approach to overcome some of the surgical drawbacks such as TH. The most common published is the use of a minipterional (MPT) approach (5). However, the minimalist approach has been debated regarding its effectiveness due to the narrowing of the visual field and restricted maneuverability (6). In the Johns Hopkins experience a retrospective review performed by Huang et al. found the MPT a suitable alternative approach without suboptimal visualization and no instances of improper vascular clip applications (7). They also described limited temporal wasting in 96% of their patients. The obvious limitations to this study and much of the studies in the literature are that they are retrospective in design. Additionally, the primary objective of that study was to evaluate the safety and efficacy of a minimalist approach. To their credit the temporal hollowing was addressed with a placement of an artificial implant. To date there has not been a prospective study regarding the reconstructive placement of the bone flap and temporalis muscle after a pterional approach to the cranium. Elucidation of a surgical cause of TH may lead to a decrease in secondary surgeries and the inherit risks that are associated.

3. Study Procedures

This study will include all patients under the care of [name] MD who qualify for a pterional approach for management of their neurosurgical disease. A pre-operative CT scan will be performed using the Gordon/Stryker Maxillofacial protocol, which is performed as part of the patients routine workup. If

Date: 10/24/2017
Principal Investigator: [name]
Application Number: IRB00120812

the patient agrees to take part in the study, the patient will be randomized into 1 of 2 groups (randomization will take place by a coin flip).

Group Heads: Traditional pterional approach with a muscle cuff left for TMS

Group Tails: Traditional pterional approach with TMS performed with a bone plate.

All patients will be assigned a confidential experimental number which will be linked to their MRN. The linking database identifying patients with their alphanumeric code will be stored on a single computer that is password protected. The password will only be given to the Co-Investigators on this IRB application.

Routine follow up will be performed at 1 week from surgery, 1 month, and lastly 6 months from surgery where a routine post-operative CT Scan will be performed.

Photographs will be taken on the lateral head for comparison. All identifying markers (eyes, nose, and lips, or skin lesions/tattoos) will be removed for privacy. All other care and services will be as per routine.

There will be no extra research procedures performed or asked of the patient.

Demographic data including age, gender, indication for surgery, length of surgical time, and complications will be recorded.

a. Study Duration

- a. The duration of the study will conclude 6 months after the last patient is enrolled. The study does not alter the normal amount of post-operative visits that are considered routine.

b. Blinding, including justification for blinding or not blinding the trial, if applicable.

There will be no blinding of the study as the operating surgeon will need to know which operation to perform.

c. Justification of why participants will not receive routine care or will have current therapy stopped.

- a. All patients enrolled will receive routine care

d. Justification for inclusion of a placebo or non-treatment group.

- a. There will be no role for a placebo group or a non-treatment group, as standard of care is some form of TMS

e. Definition of treatment failure or participant removal criteria.

- a. Participant removal will be initiated if they are unwilling to follow up in a routine fashion as outlined in the study protocol.

f. Description of what happens to participants receiving therapy when study ends or if a participant's participation in the study ends prematurely.

- a. All patients under the care of [name] will receive routine care and followup. This includes management of all surgical complications. There is no alteration of their routine care when the study ends or is prematurely ended.

4. Inclusion/Exclusion Criteria

This study will include all patients over the age of 18 years who qualify for a pterional approach for their neurosurgical pathology. This will be determined by a clinical exam and plan by [name].

We will not include patients from protected populations, such as inmates or children. Patients will not be excluded on the basis of pregnancy.

5. Drugs/ Substances/ Devices

- a. The rationale for choosing the drug and dose or for choosing the device to be used. **N/A**
- b. Justification and safety information if FDA approved drugs will be administered for non-FDA approved indications or if doses or routes of administration or participant populations are changed. **N/A**
- c. Justification and safety information if non-FDA approved drugs without an IND will be administered. **N/A**

6. Study Statistics

- a. Primary outcome variable.
The primary end point and outcome variable will be the CT quantitative evaluation of TH. The pre and post operative CT scans will be analyzed by the same volume dimensional analysis which has been previously standardized by the lead authors' prior study on TH and cranioplasties (8). Percent change and volume analysis as compared to the non operated temporal region in a two dimensional and three dimensional view will be the primary outcome variable.
- b. Secondary outcome variables.
Secondary variables will include patient satisfaction for aesthetic results. Patients will be asked to rate their satisfaction of their aesthetic result on a scale from 1 to 10.

Date: 10/24/2017
Principal Investigator: [name]
Application Number: IRB00120812

- c. Statistical plan including sample size justification and interim data analysis.
A sample size of 30 patients was calculated (alpha error of .05 and a statistical power of 0.80) in order to detect a significant difference in post-operative TH in the 2 different surgical techniques. A paired Student t-test will be used to compare the degree of TH on the control side with the operated side. For the categorical data, a Fisher test and chi square test will be utilized. Differences less than 0.05 will be considered significant.
- d. Early stopping rules.
The study will be stopped early if patients with a certain type of TMS have favorable results.

7. Risks

- a. Medical risks, listing all procedures, their major and minor risks and expected frequency.
 - 1. There are no added risks to this study
- b. Steps taken to minimize the risks. **N/A**

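### The coin is flipped when the patient agrees, although the arms do not differ until the muscle is elevated, so patients can be lost after randomisation with the allocation already known

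*Combined protocol and SAP*

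**What the plan says.** **Timing.** Section 3 states that if "the patient agrees to take part in the study, the patient will be randomized into 1 of 2 groups", and that a coin decides. It does not give the interval from agreement to surgery.

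**Arms.** Section 3 defines them as "Group Heads: Traditional pterional approach with a muscle cuff left for TMS" and "Group Tails: Traditional pterional approach with TMS performed with a bone plate".

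**Where they diverge.** Section 2 (Surgical Details/Anatomy) describes the choice as an intra-operative step that precedes the craniotomy: "Either the entire temporalis muscle can be elevated or a cuff of temporalis muscle can be left on the cranium to facilitate closure".

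**Blinding.** Section 3b: "There will be no blinding of the study as the operating surgeon will need to know which operation to perform". Nothing in section 3 withholds the coin result until the operation.

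**Eligibility.** Section 4 takes adults who qualify for a pterional approach, judged by clinical examination and plan.

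**Data and analysis.** Section 3 says "Demographic data including age, gender, indication for surgery, length of surgical time, and complications will be recorded". The technique performed is not named there. Section 6c defines no analysis set. The only removal rule (3e) concerns unwillingness to attend routine follow-up.

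**The concern.** Randomisation makes the arms comparable at the moment of the flip. Anything that removes a patient afterwards can undo this if it depends on the assignment. Here the flip comes earlier than it needs to. Before the muscle is elevated, both arms have the same operation, so an earlier flip gains nothing for the comparison of techniques, yet it opens a period in which patients can drop out of the comparison.

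A patient whose operation is cancelled or whose approach changes in that period has no pterional closure to evaluate. The primary outcome in 6a compares the operated with the non-operated temporal region, and the late CT is timed from surgery, so this patient has no relevant outcome. Analysis by assigned group cannot recover an outcome that does not exist. Because the allocation may be known and the surgeon is unblinded, the documents do not exclude that a change of plan is influenced by the coin result.

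A second, smaller gap is that the plan does not say how a patient is analysed whose closure differs from the assigned one.

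**Working it through.** **1. Order of events**

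| Step | Place | Do the arms differ yet? |
|---|---|---|
| Eligibility by examination and plan | Section 4 | No |
| Agreement, then coin flip | Section 3 | No |
| Interval to surgery, length not given | not stated | No |
| Incision, temporalis fascia divided | Section 2 | No |
| Muscle elevated, with or without a cuff left | Section 2 | **Yes, first point** |
| Craniotomy, flap fixation, muscle suspension | Section 2 | Yes |

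The flip can therefore move to just before the muscle is elevated. It cannot wait until closure, because by then the cuff has or has not been left.

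**2. The plan's own figure.** Section 6c gives 30 patients, alpha 0.05 and power 0.80, with no difference, SD or allowance for losses. The 30 cannot be reproduced. Solving backwards for 15 per arm and a two-sided two-sample comparison (both assumptions; for the CT measure 6c names a paired test of operated against control side):

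- Normal approximation: d = (1.960 + 0.842) × √(2/15) = 2.802 × 0.365 = 1.02 SD.
- Noncentral t: d = 1.06 SD.

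One patient is 1/15 = 6.7% of an arm.

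**3. What-if: losses after the flip.** Assume no true difference, k of 15 patients in each arm with g SD more hollowing, and all k lost from one arm only. The false difference is g × k/15.

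- k = 1, g = 1: 1/15 = 0.07 SD.
- k = 3, g = 1: 3/15 = 0.20 SD, or 0.20/1.06 = 19% of the detectable difference. In a simulation of 20,000 trials with 20% such patients, the false-positive rate was 0.075.
- Losses unrelated to the assignment: 0 SD, with only a smaller sample.

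**4. What-if: a changed closure.** Again no true difference, with k of 15 patients moved from the cuff to the plate group and g SD worse. If patients were grouped by technique used, the false difference is g × 2k/(15 + k).

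- k = 3, g = 1: 6/18 = 0.33 SD, or 31% of 1.06 SD. The simulated false-positive rate was 0.117.
- Range: with k = 1 and g = 0.5 it is 0.06 SD, with a false-positive rate of about 5%. With k = 5 and g = 2 it is 1.00 SD, with about 47%.
- Grouped as assigned (20% such patients, g = 1): 0.00 SD, with a rate of 0.052.

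**5. Price of analysing as assigned.** If a fraction f of one arm receives the other technique, d becomes 1.06 × (1 − f), and the total needed to keep 0.80 power is 30/(1 − f)².

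| f | d (SD) | Power | Total for 0.80 power |
|---|---|---|---|
| 0 | 1.06 | 0.80 | 30 |
| 6.7% | 0.99 | 0.74 | 34 |
| 10% | 0.95 | 0.71 | 37 |
| 20% | 0.85 | 0.61 | 47 |

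The values of k, g and f are illustrations. None comes from the documents.

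**The case against.** The strongest reply is that nothing in the documents shows that a patient will be lost or that a closure will change. No rate of cancellation, change of approach or change of technique is given. The interval to surgery may be short: section 3a ends the study six months after the last enrolment, while the last visit is six months after surgery, as if the two dates were close. Randomising at agreement is not in itself invalid, and the surgeon must know the assignment before the muscle is elevated. All of this stands. It makes the size of the problem unknown, but it does not give a reason for the early flip.

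A further reply is that moving the flip does not prevent a change of closure decided later in the operation, and that in the what-if analysis by assigned group alone removes that bias. This also stands, and it is why the analysis rule belongs in the fix. It does not help patients who have no pterional closure at all.

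Three stronger readings are tempting, and the documents support none of them:

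- A reader might infer that changes would run mainly from cuff to plate, in patients with poor muscle. Section 2 presents the options neutrally. It says nothing about a cuff failing or about muscle quality deciding what is feasible.
- A reader might infer that the site would sort patients by the closure used, because the arms are described by technique. The groups are also named after the coin result, which fits analysis by assignment at least as well, and no rule is stated either way.
- A reader might infer that the technique goes unrecorded. The list in section 3 is open and labelled demographic. It also omits the CT measure and the satisfaction score, which are clearly collected. The technique is unnamed, which is less than unrecorded.

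**Conclusion.** The point holds in a limited form. The flip is placed earlier than the design requires, and patients can be lost between it and the point where the arms differ, with the allocation already known to an unblinded team. At about 15 per arm, a few such patients would matter.

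The size and direction of any bias are unknown. The 0.20 SD and 0.33 SD figures are what-ifs with assumed numbers of patients and an assumed 1 SD worse outcome. They also presume 15 per arm and a two-sample test that 6c does not name, and they should not be quoted as estimates for this trial. The conclusion itself rests only on the stated order of events, the absence of blinding and the small sample.

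This is a worthwhile and inexpensive change to make before enrolment. It is not a flaw that invalidates the trial.

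**What to change.** **Main change, section 3.** Keep consent where it is. Move the coin flip to theatre, once the pterional approach is confirmed and immediately before the temporalis muscle is elevated. Losses before that point then occur before randomisation and cannot depend on the assignment.

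**Supporting text.**

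- Section 3: add to the recorded data the technique assigned, the technique performed, and the reason for any difference.
- Section 6c: state that the between-technique comparison is by assigned group, whatever closure was used, with technique performed as a sensitivity analysis only.

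**Cost.** Protocol wording and a few recorded items, with no extra patients or study procedures. The surgeon learns the assignment only at the start of the operation, and someone must perform and document the flip in theatre. Keeping patients as assigned dilutes a true difference: about 6 points of power for one changed closure in 15, and more if there are several. A change of closure made after the muscle has been elevated remains possible. The new text does not prevent it, but makes it visible and fixes how it is analysed.

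### The coin-flip allocation has nothing that fixes or logs the result in an unblinded trial; a pre-generated, concealed and logged list would make it verifiable at little cost

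*Combined protocol and SAP*

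**What the plan says.** Section 3 (Study Procedures) states that once a patient agrees to take part, "the patient will be randomized into 1 of 2 groups (randomization will take place by a coin flip". The two faces of the coin define the arms: "Group Heads: Traditional pterional approach with a muscle cuff left for TMS" and "Group Tails: Traditional pterional approach with TMS performed with a bone plate".

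Section 3b (Blinding) says: "There will be no blinding of the study as the operating surgeon will need to know which operation to perform". Section 3 also says "This study will include all patients under the care of" one named physician, and Section 4 says of eligibility "This will be determined by a clinical exam and plan by" a named clinician. The names are removed from the public copy.

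Section 6c gives the size: "A sample size of 30 patients was calculated", with alpha 0.05 and power 0.80. No effect size, standard deviation, allocation ratio or sidedness is stated. The document describes no allocation sequence, concealment, blocking, stratification or allocation log. Section 3 does give each patient a confidential study number linked to the medical record number.

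**The concern.** Sound allocation needs two things. The next assignment must be unknown when the patient is enrolled, and the assignment must be fixed and traceable once it is revealed. A fair flip after agreement meets the first. Nothing in the protocol secures the second.

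A coin leaves no sequence to check against. If a result is flipped again, or a patient is quietly not counted after an unwelcome result, no trace need remain. The trial is open, so the people involved know each result as it arises. Section 3e also allows removal of participants who will not follow up, and no section requires an account of everyone allocated.

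The comparison of the two suspension techniques rests on the arms being alike at baseline. With about 15 patients per arm, moving a few patients can create or hide a difference. The protocol criticises earlier work for being retrospective, and verifiable random allocation is much of what would set this trial apart. A second, smaller matter is that 30 simple flips often give unequal arms.

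**Working it through.** **Inputs.** From the protocol: coin flip (Section 3); total of 30, alpha 0.05, power 0.80 (Section 6c). Assumed: a fair coin, 30 as the total over both arms, a two-sided between-arm t-test with equal variances, and no dropout. Section 6c names only a paired t-test of operated against control side, so the between-arm test is an assumption.

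**1. The plan's own figure.** N = 30 cannot be reproduced, because no effect size or SD is given. It can only be back-solved. With arms n1 and n2 and standardised difference d, the noncentrality is d × √(n1·n2/(n1+n2)). At 15:15 the multiplier is √7.5 = 2.739. With 28 degrees of freedom, 80% power needs a noncentrality of 2.902, so d = 2.902/2.739 = 1.06. (A one-sided test gives 0.93; the normal approximation gives 1.02.)

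**2. Imbalance under the coin, and power at each split.** P(larger arm ≥ k) = 2 × Σ C(30, x)/2³⁰ for x from k to 30, with k above 15. Power holds d at 1.06; for example, at 20:10 the noncentrality is 1.06 × √(200/30) = 2.74.

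| Split | Chance of this or worse | Power at this split |
|---|---|---|
| 15:15 (exactly) | 14.4% | 80.0% |
| 17:13 | 58.5% | 79.3% |
| 18:12 | 36.2% | 78.4% |
| 19:11 | 20.0% | 77.0% |
| 20:10 | 9.9% | 75.2% |
| 21:9 | 4.3% | 72.8% |

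For 15:15 the chance is that of the exact split. Weighted over all splits, power averages 78.6%, a loss of 80.0 − 78.6 = 1.4 points.

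**3. What blocking buys and costs.** With fixed blocks of 4, the worst final split of 30 is 16:14 (probability 1/3), where power is 79.8%. The cost is predictability. Someone who sees past assignments guesses the arm with fewer patients so far, and tosses up when level. In a block of 2b the expected number of correct guesses is b + (4ᵇ/C(2b, b) − 1)/2:

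- block of 2: 1.5 of 2 (75%)
- block of 4: 2.83 of 4 (70.8%)
- block of 6: 4.1 of 6 (68.3%)

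Sizes 2, 4 and 6 in equal proportion give (1.5 + 2.83 + 4.1)/12 = 70.3% over complete blocks. Simulation of a list of 30 gives about 70%. Sizes 4 and 6 alone give (2.83 + 4.1)/10 = 69.3%. A fair coin gives 50%.

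**4. Illustration of steering (assumed numbers only).** Suppose k patients with prognosis 1 SD worse all end in one arm of 15 and the techniques do not differ. The shift in means is k/15 SD, and the noncentrality is (k/15) × 2.739.

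| k | Shift (SD) | Noncentrality | Two-sided type I error |
|---|---|---|---|
| 1 | 0.067 | 0.18 | 5.4% |
| 2 | 0.133 | 0.37 | 6.4% |
| 3 | 0.200 | 0.55 | 8.3% |

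This treats the bias as a pure shift in means. If the three patients also widen the spread in their arm, simulation puts the last figure at about 7.0%.

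**The case against.** The best defence is that a fair flip made after the patient agrees gives no foreknowledge at enrolment. Who judges eligibility then matters little, and the lack of blinding concerns what is known after allocation. That stands. What remains is re-flipping or discarding a result, which would be a deliberate departure from the protocol, and no document suggests that anyone intends it or prefers one technique. The steering figures are therefore illustrations, not estimates.

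A dated, witnessed log of flips could also close most of the gap without giving up the coin. That stands in part. A log shows what was entered, but a flip made before the entry leaves nothing behind, whereas a skipped number on a list fixed in advance is visible.

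Four stronger readings are tempting and are not supported:

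- *The flips go unrecorded.* The protocol is silent on recording; it does not say that none is kept.
- *The surgeon who judges eligibility also operates and flips the coin.* The names are removed and the person flipping is never identified, so the text does not show that these are one person.
- *Unequal arms seriously weaken the trial.* They are common, but the average loss is about 1.4 power points.
- *A blocked list cures everything.* In an open trial, blocking adds predictability that the coin does not have, and varying the block sizes removes little of it.

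**Conclusion.** The point holds as a gap in verifiability. As written, nobody could show that each flip was made once, after enrolment, and kept. This is worth correcting because the safeguard is cheap and cannot be added once patients have been allocated.

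The size of any bias is unknown. Under the assumed steering of one to three patients, the type I error would be about 5.4% to 8.3%. Imbalance is secondary: a 36% chance of 18:12 or worse, with average power of 78.6% against 80%. Those power figures rest on d = 1.06, which is back-solved from N = 30 and is not a figure in the plan. The documents do not support a claim that allocation was or will be manipulated.

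**What to change.** Replace the coin flip in Section 3 with the following:

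- a computer-generated 1:1 list, prepared in advance by an existing team member who neither enrols nor operates;
- assignments kept in sequentially numbered, opaque, sealed envelopes or an equivalent locked file;
- each assignment opened only after consent and confirmed eligibility, and logged with the date and the study number;
- every opened assignment accounted for in the report, including patients later removed.

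Blocking is optional. An unblocked concealed list keeps assignments unpredictable and accepts the loss of about 1.4 power points. If blocks are used, their sizes should be undisclosed and larger than 2, with the remaining guessability acknowledged.

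The cost is a few hours of set-up and a short change to the protocol, assuming the team has a member free of both enrolment and surgery. Patient care, visits and sample size do not change. Any patients already allocated by coin should be reported as such, with whatever record of their allocation exists.

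### Study end is counted from the last enrolment but the primary-endpoint CT from surgery, so the last patient's scan may fall after the stated end of the study

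*Combined protocol and SAP*

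**What the plan says.** Five statements in the combined protocol and SAP bear on this.

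- **Study end (section 3.a).** "The duration of the study will conclude 6 months after the last patient is enrolled". The clock starts at enrolment.
- **Final visit and CT (section 3, follow-up schedule).** After visits at 1 week and 1 month, the schedule is "lastly 6 months from surgery where a routine post-operative CT Scan will be performed". The clock starts at surgery. No visit window is given, and no other post-operative CT is scheduled.
- **Primary endpoint (section 6.a).** "The primary end point and outcome variable will be the CT quantitative evaluation of TH". Pre-operative and post-operative scans are compared. The section names no time point.
- **Order of events (sections 3 and 3.b).** Once the patient agrees to take part, "the patient will be randomized into 1 of 2 groups (randomization will take place by a coin flip". The two groups differ in how the temporalis muscle is resuspended. Section 3.b explains the open design in this way: "There will be no blinding of the study as the operating surgeon will need to know which operation to perform".
- **After the study (section 3.f).** "There is no alteration of their routine care when the study ends or is prematurely ended".

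The documents do not define the date of enrolment. They give no interval from enrolment to surgery, and they do not say whether scans done after the study has ended are collected or analysed.

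**The concern.** The end of the study and the endpoint visit are both 6 months long but start from different events. The event that starts the study-end clock comes first, or at best on the same day. Read as written, the rule can close the study before the last patient is due for the scan on which the primary comparison rests.

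At stake is the status of those scans. A scan done after the stated end has no rule in the plan saying whether it counts. The team would have to decide at the end of the trial, in an unblinded study, whether to include it. A team that wanted to respect the date could instead bring the scan forward. That would shorten the observation period, although the protocol's opening paragraph describes hollowing as generally appearing within 6 months of surgery. The satisfaction rating in section 6.b has no stated time point; if it is taken at the final visit, it has the same problem.

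**Working it through.** The documents show no derivation of the study duration, so there is no figure of the plan's own to reproduce. The check is calendar arithmetic.

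**Inputs**

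- E = date on which the last patient is enrolled (section 3.a).
- S = date of that patient's surgery (section 3).
- L = lateness of the CT relative to exactly 6 months. The protocol gives no window, so L is unknown; L = 0 means on time.

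**Step 1: is the 6-month CT the endpoint scan?** Section 6.a needs a post-operative CT and section 3 schedules only one. This is an inference, but the documents offer no other candidate.

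**Step 2: order of enrolment and surgery.** The allocation determines the closure technique and the surgeon must know it in order to operate. Hence E cannot be later than S, and S − E ≥ 0.

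**Step 3: overrun for the last patient.**

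- Study end = E + 6 months
- Endpoint CT = S + 6 months + L
- Overrun = (S + 6 months + L) − (E + 6 months) = (S − E) + L

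The 6 months cancel. With an on-time scan the overrun is simply the gap from enrolment to surgery. The documents do not give this gap, so the following range is assumed:

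| Assumed gap S − E (days) | Overrun with an on-time CT (days) |
|---|---|
| 0 | 0 |
| 1 | 1 |
| 7 | 7 |
| 14 | 14 |
| 30 | 30 |
| 60 | 60 |

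The overrun is zero only when enrolment and surgery fall on the same day and the scan is done at exactly 6 months. A late scan adds its delay to each row.

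**Step 4: who else is affected?** For another patient operated on at S₂ and scanned on time, the CT falls after study end when S₂ + 6 months > E + 6 months, that is when S₂ > E. The patients affected are therefore those operated on after the last enrolment date. Their number depends on the accrual rate and the gap, neither of which is given, so it cannot be computed.

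**Step 5: effect of the proposed wording.** If study end is defined as completion of the last 6-month post-operative visit and CT, the overrun is 0 by construction, whatever the gap or the lateness.

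**The case against.** The strongest case on the other side has three parts.

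**The date is a description and not a data cut-off.** Section 3.a gives a duration, and its next sentence is about the number of routine visits. It can fairly be read as saying that follow-up lasts 6 months. If the end date barred all later study work, the CT measurement and the statistical tests could not be done either, even with a zero gap. This stands as an argument against the harshest reading. It does not remove the mismatch, because the date as stated still comes on or before the visit it is meant to cover.

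**The scan would happen anyway.** The 6-month CT is described as routine, section 3 adds no research procedures, and section 3.f keeps routine care unchanged after the study ends. This stands in full. The risk is a scan outside the stated study period; it is not a scan that is never done.

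**The gap may be nil.** The protocol's opening paragraph lists trauma and vascular insults among the indications. The pre-operative CT is described before the patient agrees, which suggests, without proving, that enrolment comes late in the workup. With same-day surgery and an on-time scan, the CT falls on the end date itself. This also stands, and it makes the finding conditional. But section 2 also names suprasellar lesions and medial sphenoid wing tumours, and nothing requires enrolment and surgery on the same day.

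A reader might go further and infer that endpoint data are lost by rule, or that the planned number ("A sample size of 30 patients was calculated (alpha error of .05 and a statistical power of 0.80") cannot be reached and power falls. The documents do not support this. No passage excludes later scans. Putting a figure on a power loss would also need an effect size and an arm split that section 6.c does not state, and the coin flip does not fix the split.

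**Conclusion.** The point holds in a conditional form. Sections 3 and 3.a count from different events, enrolment cannot follow surgery, and the stated end leaves no slack. If the last patient has any gap between enrolment and surgery, or a late scan, that patient's primary-endpoint CT falls after the stated study end. The same may be true of any other patient operated on after the last enrolment date.

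In time, the size is the gap plus any lateness. In patients, it is probably one or a few, but the documents do not allow a count. No loss of data or power is demonstrated. The conclusion rests on two readings: that the 6-month scan is the endpoint scan, and that enrolment is no later than randomisation. Both follow closely from the text.

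Severity is minor. This is nevertheless more than a missing detail, because the end rule conflicts with the plan's own endpoint schedule.

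**What to change.** Reconcile section 3.a with the follow-up schedule in section 3. Suggested wording for 3.a: *The study concludes when the last enrolled patient has completed the 6-month post-operative visit and CT.* Because the last patient enrolled need not be the last operated on, the text should make clear that it means the last such visit among all enrolled patients.

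The cost is one sentence and a slightly later closing date. No visit, scan or procedure is added, since the CT is already part of routine care.
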